4. STUDY POPULATION

4.1 Population (base)

Adult patients, both males and females, qualifying for instrumented posterolateral spinal fusion of one to six levels between T10 and S2 with the use of autograft will be recruited by their treating orthopaedic surgeon or his/her assistant at the UMC Utrecht, OLVG Amsterdam, St. Antonius Hospital Utrecht, Rijnstate Arnhem or Amphia Hospital Breda. All patients will have had at least one conservative treatment attempt prior to enrollment. Based on the sample size calculation described in Paragraph 4.4 and Appendix A, the total number of patients to be enrolled is 100. Based on our experience with the AxA study, patient enrollment is expected to take two years.

4.2 Inclusion criteria

In order to be eligible to participate in this study, a patient must meet all of the following criteria:

- To be treated with instrumented posterolateral thoracolumbar spinal fusion with the use of iliac crest bone, with or without additional posteriorly inserted interbody devices (PLIF, TLIF), because of (1) deformity, (2) structural instability and/or (3) expected instability as a result of decompression for spinal stenosis;
 1. Deformity is defined as a scoliosis in the coronal plane of $>20^\circ$ and/or a sagittal balance disturbance according the SRS/Schwab classification³³ on standardized standing full spine radiographs;
 2. Preoperative instability is defined as a progressive angular deformity or spondylolisthesis in standing radiographs;
 3. Decompression for spinal stenosis is done in the occurrence of radiological evidence of stenosis on MRI and clinical leg and/or back pain with one or more of the following phenomena: radiculopathy, sensory deficit, motor weakness, reflex pathology or neurogenic claudication.
- Non-responsive to at least 6 months of non-operative treatment prior to study enrollment;
- Fusion indicated for one to six levels in the T10 to S2 region. In case of vertebral osteotomies (PSO or VCR) the osteotomized segment will not be included in the assessment of the fusion rate;
- Willing and able to understand and sign the study specific Patient Informed Consent;
- Skeletally mature between 18 and 80 years of age.

4.3 Exclusion criteria

A potential subject who meets any of the following criteria will be excluded from participation in this study:

- Any previous surgical attempt(s) for spinal fusion (revision surgery) of the intended segment(s);
- Previous treatments that compromise fusion surgery like irradiation;
- Previous autologous bone grafting procedures that compromise the quality and amount of iliac crest bone grafting;
- Indication for spinal fusion because of an acute traumatic reason, like a spinal fracture;
- Active spinal and/or systemic infection;
- Spinal metastasis in the area intended for fusion;
- Systemic disease or condition, which would affect the subjects ability to participate in the study requirements or the ability to evaluate the efficacy of the graft (e.g. active malignancy, neuropathy, pregnancy);
- At risk to be non-compliant e.g.: (recently treated for) substance abuse, detainee, likely to immigrate
- Participation in clinical trials evaluating investigational devices, pharmaceuticals or biologics within 3 months of enrollment in this study;
- Female patients who intend to be pregnant within 1.5 year of enrollment in the study;
- Body mass index (BMI) larger than 36 (morbidly obese);
- Being expected to require additional surgery to the same spinal region within the next 6 months;
- Current or recent (<1yr) corticosteroid use equivalent to prednisone ≥ 5 mg/day, prescribed for more than 6 weeks.

4.4 Sample size calculation

The primary objective of this study is to demonstrate that treatment with MagnetOsTM Granules is non-inferior to autograft to obtain bony fusion in the spine. The primary outcome is the rate of successful posterolateral bony fusion after one year, assessed at CT-scans. Fusion will be scored binomially and non-inferiority of fusion in the MagnetOs condition will be assessed using a McNemar's test.

Based on literature^{6,28-30,34} and the preliminary results of the AxA study, we estimate a fusion percentage of 50% for unilateral grafting after one year, and a 70% concordance between the left and right side of the fusion trajectory (i.e. both sides fused or non-fused). The non-

inferiority margin is set at an absolute 15% less effectiveness in the MagnetOs condition after one year, which corresponds with 15% less posterolateral sides that are judged as fused. In other words, the rate of fused posterolateral sides in the MagnetOs condition should be more than 35% if the autograft condition shows 50% fusion. We argued that the percentage of the iliac crest graft related complications, ranging from 5% major complications to 40% minor complications, may justify 15% less fusion in a condition that eliminates these complications.

Based on a 1:1 paired assignment of MagnetOsTM Granules to the control condition with autograft, a power of 80%, a one-sided alpha of 0.05 and the non-inferiority margin of 15%, the required sample size for the primary outcome is 84 patients (see Appendix A). We assume that approximately 15% of the included patients will not be evaluable after one year. The intra-patient analyses are not possible when the fusion area has to be revised or when a deep wound infection has occurred and considerable amounts of graft material have to be removed (expected percentage 2-5%). Other failures are lost to follow-up or bad scan quality. Therefore, the total number of patients to be enrolled will be 100.

5. TREATMENT OF SUBJECTS

As explained in the introduction, autologous bone grafting is the gold standard to achieve bony fusion in (instrumented) spinal fusion procedures. In this study, according to a randomization scheme, one side of the spine will be grafted with the synthetic ceramic material MagnetOsTM Granules instead of local bone mixed with bone harvested from the iliac crest. The rest of the surgical procedure will be according to standard care. The investigational product is described more detailed in the next Chapter; the treatment procedure and follow-up are described in Chapter 7.

6. INVESTIGATIONAL PRODUCT

6.1 Name and description of investigational product

MagnetOsTM Granules is a synthetic ceramic that has a CE-mark (2115660CE01) as well as FDA 510(k) clearance (K161859). It is comprised of calcium phosphate granules with a tricalcium phosphate (β -TCP) and hydroxyapatite (HA) ratio of 70/30. The calcium phosphate granules have shown to be bioactive, osteoconductive and osteoinductive.¹¹

MagnetOsTM Granules is intended for use as a bone void filler for voids and gaps of the skeletal system that are not intrinsic to the stability of the bony structure, and not too large that they would fail to heal spontaneously in the surgeon's opinion. The device may be combined with autogenous bone, blood, platelet-rich plasma, and/or bone marrow. In load-bearing situations, MagnetOsTM Granules is to be used in conjunction with internal or external fixation devices.

6.2 Summary of findings from non-clinical studies

Biocompatibility of MagnetOsTM Granules has been established through testing and evaluation per ISO 10993 standards for permanent implant contacting bone/tissue. The material was found to be non-cytotoxic, non-sensitizing, non-irritating, non-genotoxic, and non-toxic.

To test device performance, MagnetOsTM Granules has been compared to predicates including AttraX Granules (a.k.a. CuriOsTM), VitossTM BA (Orthovita) and ActifuseTM ABX (Apatech) in a series of benchtop and animal studies. Benchtop degradation tests show that MagnetOsTM Granules are resorbable. The resorption rate of MagnetOs is situated within the range of other commercially available calcium phosphate bone void fillers. From the quickest to slowest resorbable material: Vitoss>AttraX>MagnetOs>Actifuse ~ Pro-Osteon ~ OsSatura. Testing of the structure of the calcium phosphate components using mercury intrusion porosimetry showed that MagnetOsTM Granules have a total porosity of 70±15%. The total surface area of MagnetOsTM Granules is larger than that of CuriOsTM, VitossTM BA and ActifuseTM ABX. These surface features have shown to be important in promoting bone formation.

Ectopic implantation in a dog intramuscular model showed the osteoinductive potential and biocompatibility of MagnetOsTM compared to OsOpia (REGEDENT AG) and CuriOsTM. After 12 weeks implantation, no necrosis and inflammation were seen in any of the explants. MagnetOsTM gave rise to earlier bone formation than CuriOsTM and OsOpia^{14,15} while bone%

and cellular activity on the different microstructures were equivalent for all groups at 12 weeks.

Two preclinical studies in spine posterolateral models showed efficacy of MagnetOs™ Granules. In a sheep model of instrumented posterolateral spinal fusion, of MagnetOs™ Granules with or without a binder showed to have similar fusion rates at different time points compared to autograft. At 12 weeks, the fusion rate assessed by manual palpation and histology showed a high fusion performance (see table 1). The tissue responses were similar for all implanted bone grafting materials. Material resorption and bone formation were quantified by histomorphometry. An equivalent amount of bone was formed and a slower resorption of MagnetOs™ Granules was observed, as compared to CuriOs™ granules. Distant organs and blood analyses confirmed the lack of systemic toxicity.¹⁶

Table 1. Fusion by histology (instrumented Sheep spine posterolateral fusion)

U=unilateral fusion; B=bilateral fusion; FR=Fusion rate. BCP= MagnetOs

	6 wks			12 wks			26 wks		
	U	B	FR	U	B	FR	U	B	FR
Autograft	1/5	0/5	10%	1/6	4/6	75%	1/5	4/5	90%
BCP	0/5	0/5	0%	1/6	5/6	92%	0/5	5/5	100%
BCP + Binder	0/5	0/5	0%	2/6	4/6	83%	1/5	4/5	90%

As an autograft extender, MagnetOs™ Granules achieved similar fusion rates compared to autograft alone in a rabbit bilateral un-instrumented posterolateral spinal fusion. At 6, 9 and 12 weeks, the animals were essentially equivalent based on all end point evaluations (manual palpation, radiography, micro-CT, histology). Progression of fusion was also seen for all end points at 6, 9 and 12 weeks. Mechanical testing (flexion-extension and lateral bending) at 12 weeks demonstrated fusion of the treated level, which was comparable to the autograft group and in line with the manual palpation results. Histology and histomorphometry versus time demonstrated the normal features of bone healing and progression to spinal fusion. An osteoconductive response was noted at 6 weeks with newly formed bone formation both on and between the resorbing calcium phosphate mineral as well as with the residual autograft particulate. The normal concert of new bone formation, implant resorption and remodeling occurred with time as the newly formed bone remodeled together the material resorption and normal marrow spaces developing to mature fusion space at 12 weeks. No adverse reactions were observed.

Table 2. Fusion by histology (Rabbit spine posterolateral fusion)

	Histological fusion		
	6 weeks	9 weeks	12 weeks
Autograft(AG)	0% fus	20% fus	60% fus
MagnetOs TM Granules/AG	10% fus	20% fus	70% fus
MagnetOs TM Putty/AG	10% fus	20% fus	60% fus

6.3 Summary of findings from clinical studies

No clinical investigations of MagnetOsTM Granules have been performed to-date.

6.4 Summary of known and potential risks and benefits

Spinal fusion with a synthetic bone graft substitute is a widely available surgical treatment option for patients with a spinal deformity. However, there are some short and long-term risks that one has to be aware of.

Short term risks of a bone graft substitute include, but are not limited to:

- Migration of the device from the site of implantation
- An allergic reaction to the implanted material

Long term risks of a bone graft substitute include, but are not limited to:

- Failure to promote bone fusion
- Excessive bone growth, or bone growth in unwanted locations

As mentioned above, MagnetOsTM Granules has shown in preclinical animal models to result in increased fusion potential and quicker fusion than similar commercially available materials. Potential benefits in the clinical setting might include higher fusion rates, and faster fusion times than other synthetics, as well as lower complications than autograft, allograft, or protein-based treatment options. This study is designed to show non-inferiority of MagnetOsTM Granules as compared to autograft for posterolateral spinal fusion as well as to determine potential risks in the clinical setting.

6.5 Description and justification of route of administration and dosage

In this study, MagnetOsTM Granules will be used as an alternative to autograft for instrumented posterolateral fusion of the thoracolumbar or lumbosacral spine, to evaluate its efficacy and safety. After instrumentation and preparation of the bilateral trajectory for grafting, the recommended volume of 8-10cc of per spinal level will be placed at the randomized allocation side, without the addition of autogenous bone, blood, plasma or bone

marrow. Close contact with vital bone is important for its function as a bone regeneration material. The surgeon will place the granules around the instrumentation and in the decorticated lateral gutters, bridging the dorsal surfaces of the transverse processes, facets and laminae, without destruction of the granules structure.

6.6 Product storage and accountability

MagnetOs™ Granules will be provided by the subsidizing party in commercially available packages of 5cc (vials in a pouch). The product will be stored at each participating site according to the recommended storage conditions. Shipment and distribution records as well as product accountability logs will be retained. At the end of the study, unused products will be returned to the subsidizing party.

7. METHODS

7.1 Study outcomes

7.1.1 Primary study outcomes

1. Posterolateral spinal fusion rate at one-year follow-up (assessed on CT-scans);
2. Rate of (serious) adverse events that are related to the procedure in any way, and their potential relation with MagnetOsTM Granules.

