2. OBJECTIVES

2.1 Primary objectives

The primary objective of this study is to demonstrate the non-inferiority of MagnetOsTM Granules as compared to autologous bone graft in instrumented posterolateral fusion of the thoracolumbar and lumbosacral spine, in terms of efficacy and safety.

1. Efficacy will be based on the posterolateral spinal fusion rate assessed at one-year CT-scans;
2. Safety will be evaluated by documenting the number and nature of all (serious) adverse events that may in any way be related to the surgical procedure. The complication rate will be compared to the rate in control populations from literature.

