To investigate the efficacy of a bone graft substitute like MagnetOs™ Granules in the patient group that will benefit most from it, is challenging as these patients and surgeries are quite unique. The types of fusion in terms of location and number are highly variable and difficult to compare. Also, several surgical techniques are applied in addition to the posterolateral fusion at various levels. For example, posterior lumbar interbody fusion (PLIF) or transforaminal lumbar interbody fusion (TLIF). The solution to these impediments is to use a model where the patient is its own control. This is a recognized option in posterolateral spinal fusion investigations, because the right and left side of the spine are subject to similar procedures but physically separated.^{29,30} Moreover, the assessment of spinal fusion in terms of bone continuity and bone volume of both sides can be done independently. By using an intra-patient comparison model, the number of patients required for sufficient study power will be even less than half the number needed for traditional inter-patient comparisons. This is

because inter-patient variability of confounders for bony fusion is irrelevant with this approach. Finally, an important ethical advantage of this model is that the patient always receives the gold standard treatment for posterolateral fusion at one side of the spine, and for interbody fusion as well when an additional PLIF or TLIF procedure is performed. When the bone graft substitute would unexpectedly fail to establish a bony fusion, the implications will be much less severe because the contralateral side will have the gold standard treatment and a unilateral fusion of the spine is sufficient.

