7.3.2 Surgical and postoperative procedures

Patients will be operated according to standard surgical procedures for instrumented posterolateral fusions between T10 and S2, with the only exception that one side of the spine will be grafted with the synthetic ceramic material MagnetOs™ Granules instead of bone harvested from the iliac crest. A recommended surgical technique is provided in Appendix B. In advance, the participating orthopaedic surgeons of each center will receive instructions on appropriate use of MagnetOs™ Granules from the principal investigator. Any questions that may arise concerning the surgical aspects of using MagnetOs™ Granules or autograft will be answered by the principal investigator.

Standard prophylactic antibiotics will be given for at least 24 hours, according the local surgical guidelines of each center. A thrombosis prophylaxis will be used according to the surgeons' preference. If preferred by the surgeon, patients will receive a restraining brace or orthosis postoperatively in order to protect the spine from (excessive) movements. Mobilization will be encouraged on the first postoperative day; physiotherapy will be offered during hospitalization and ambulatory if indicated.

According to standard care, standing anteroposterior and lateral radiographs will be taken postoperatively during hospitalization.

During surgery and hospital admission, the following information will be collected (CRF B):

- Date of surgery
- Surgeon's name
- Surgical technique
 - Instrumented spinal levels
 - Levels of decompression
 - Performance of vertebral osteotomy
 - Use of interbody device
 - Insertion side of TLIF
 - Additional surgical procedures
- With the use of a 20ml syringe an estimation of the volumes (in mL) of:
 - 1) obtained local bone and 2) obtained iliac crest bone and 3) the ratio of local bone / iliac crest bone used for posterolateral fusion
 - Local bone (or mixed autograft) applied per level for interbody fusion
 - (Mixed) autograft used per posterolateral fusion level

- Estimation of volume of MagnetOsTM Granules per posterolateral fusion level (in cc)
- Iliac crest side used for bone harvesting (right/left)
- Iliac bone harvested via same incision (yes/no)
- Additional time required for bone graft harvesting (minutes)
- Allocation of MagnetOsTM Granules (left/right)
- Surgical time (skin to skin and total anaesthesia time (begin and end of sedation)
- Estimated blood loss (cc)
- Use of vancomycine powder

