- Intra-operative complications
- Postoperative X-rays
- Date of discharge
- Disease related medication use (including NSAID use)

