7.3.3 Planned follow-up moments

The subsequent follow-up moments will take place at the outpatient clinic and are based on the standard care at the UMC Utrecht. The data described below will be collected at 6 weeks, 3 months, 1 year and 2 years postoperatively. The questionnaires, CT-scan at 2 years follow-up in case of no or doubtful fusion at 1 year follow-up, and depending on the local follow-up protocol the CT-scan at one year follow-up and/or X-ray at two years follow-up, are extra for this study. In addition to the baseline questionnaires, treatment satisfaction will be assessed with a Numeric Rating Scale (NRS).

6 weeks (±14 days; CRF C)

- Complications / (serious) adverse events
- Disease related medication use (including NSAID use)
- Questionnaires
 - EQ-5D-5L
 - ODI
 - NRS satisfaction
- VAS pain score
 - Back pain related to diagnosis
 - Leg pain related to diagnosis
 - Pain in left iliac crest

- Pain in right iliac crest
- Pain drawing
- Imaging
 - Standing anteroposterior and lateral radiographs
- Radiologic evaluation by treating surgeon (indications for failure or deformation / instability)

3 months (\pm 21 days; CRF D)

- Complications / (serious) adverse events
- Disease related medication use (including NSAID use)
- Questionnaires
 - EQ-5D-5L
 - ODI
 - NRS satisfaction
- VAS pain score
 - Back pain related to diagnosis
 - Leg pain related to diagnosis
 - Pain in left iliac crest
 - Pain in right iliac crest
 - Pain drawing
- Imaging
 - Standing anteroposterior and lateral radiographs
- Radiologic evaluation by treating surgeon (indications for failure or deformation / instability)

1 year (12-15 months; CRF F)

- Complications / (serious) adverse events
- Disease related medication use (including NSAID use)
- Questionnaires
 - EQ-5D-5L
 - ODI
 - NRS satisfaction
- VAS pain score
 - Back pain related to diagnosis
 - Leg pain related to diagnosis
 - Pain in left iliac crest

- Pain in right iliac crest
- Pain drawing
- Imaging
 - Standing anteroposterior and lateral radiographs
 - CT-scan
- Radiologic evaluation by treating surgeon (indications for failure or deformation / instability)
- Fusion assessment based on CT-scan by treating surgeon per level and per side in three planes, without the distinction between graft-related or non-graft-related fusion as described in Appendix C.

2 years (22-26 months; CRF G)

- Complications / (serious) adverse events
- Disease related medication use (including NSAID use)
- Questionnaires

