7.9 Premature termination of the study

All (serious) adverse advents that can be related to the surgical procedure in any way will be reported to the principal investigator as described in Chapter 8 and evaluated. If a relation to the performance of MagnetOsTM Granules is suspected, the allocation side can be disclosed. These findings will be discussed with the METC.

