9.2 Primary safety analysis

(Serious) adverse events occurring during the study that may in any way be related to the surgical procedure will be reported in adverse event tables. The frequency and nature of events will be compared to events in control populations from literature.

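### The primary safety outcome covers the events' relation with MagnetOs, but section 9.2 plans no left-right comparison of local events and no listed event item asks for the side

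*Combined protocol and SAP*

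**What the plan says.** Section 7.1.1 lists as the second primary outcome: "Rate of (serious) adverse events that are related to the procedure in any way, and their potential relation with MagnetOsTM Granules". It has two parts, a rate and a question of relation to the product. The Summary goes further and states the primary objective as non-inferiority for efficacy and safety through the within-patient design.

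The analysis covers the first part only. Section 9.2 provides adverse event tables and then: "The frequency and nature of events will be compared to events in control populations from literature". Section 2.1 says the same: "The complication rate will be compared to the rate in control populations from literature". Appendix A has no safety analysis.

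The listed event items are single lines: "Intra-operative complications" at surgery (section 7.3.2) and "Complications / (serious) adverse events" at each follow-up visit (section 7.3.3). Sections 7.4.1 (X-ray failure signs) and 8.2 to 8.3 (event definitions, reporting and follow-up) do not mention side. The relation to the product appears in section 7.9, case by case: "If a relation to the performance of MagnetOsTM Granules is suspected, the allocation side can be disclosed".

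Side is listed elsewhere. Section 7.3.2 records the MagnetOs side, the harvest side and the TLIF insertion side. Iliac crest pain is scored left and right, and CT fusion is read per side.

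**The concern.** Part of a primary outcome has no stated analysis, and the design offers one that goes unused. Section 3 defends the within-patient design on the ground that "the right and left side of the spine are subject to similar procedures but physically separated". Section 6.4 names product risks that are local and can have a side: migration from the implantation site and bone growth where it is not wanted. Section 6.3 says there is no earlier clinical investigation of MagnetOs.

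Without a left-right table, the planned evidence on relation to the product is individual case evaluation plus published rates. Section 3 itself calls these fusions highly variable and hard to compare. A difference from the literature could then reflect the patients, the surgery or the way events were ascertained, and the planned analysis could not separate these from the graft.

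**Working it through.** **Plan's own figure.** The documents give no power or precision for safety. The only powered figure is for efficacy. With discordance 0.30 and margin 0.15, 0.30 × (1.645 + 0.842)² / 0.15² = 82.4, and an exact score calculation at N = 84 gives power 0.801 (Appendix A: 0.80098). Also 84 / 0.85 = 98.8, consistent with 100 enrolled. This reproduces but does not bear on safety.

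**What is recorded and what is analysed.**

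| Item | Side listed? | Left-right analysis planned? |
|---|---|---|
| MagnetOs allocation (7.3.2) | yes | not applicable |
| CT fusion (7.4.2) | yes | yes, efficacy |
| Iliac crest pain (7.3.1, 7.3.3) | yes | paired test of pain scores (9.3) |
| Intra-operative complications (7.3.2) | no | no |
| Adverse events at visits (7.3.3, 8.2) | no | no |
| X-ray failure signs (7.4.1) | no | no |
| CT heterotopic ossification (7.4.2) | not stated | no |

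**What a left-right comparison could show.** The documents give no side-specific event rates, so the rates below are assumptions. Let M and A be the probabilities of a local, non-donor event on the MagnetOs and autograft sides, with sides independent and n = 100.

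- One-side-only probabilities: m = M(1 − A) and a = A(1 − M).
- Number of one-side-only patients: D ~ Bin(100, m + a).
- Number of these on the MagnetOs side: X given D ~ Bin(D, m/(m + a)).
- Exact McNemar: reject when twice the smaller tail of Bin(D, ½) is at most 0.05.

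| A | M | a | m | Two-sided power |
|---|---|---|---|---|
| 1% | 3% | 0.0097 | 0.0297 | 0.03 |
| 2% | 5% | 0.0190 | 0.0490 | 0.10 |
| 2% | 8% | 0.0184 | 0.0784 | 0.37 |
| 2% | 10% | 0.0180 | 0.0980 | 0.58 |
| 2% | 12% | 0.0176 | 0.1176 | 0.75 |

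If the rates are read directly as one-side-only rates, 5% against 2% still gives 0.10 and 10% against 2% gives 0.56.

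In terms of counts, a 6:0 split gives p = 2 × 0.5⁶ = 0.031, a 5:0 split gives 0.0625, and a 9:1 split gives 2 × 11/1024 = 0.021. No events on the MagnetOs side in 100 patients gives a one-sided 95% upper limit of 1 − 0.05^(1/100) = 3.0%.

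**Against the literature, same events.** Take the same class of event with a literature rate of 2% + 2% = 4%, treated as exactly known, and 2% + 10% = 12% here (ignoring patients with events on both sides). A one-sample exact test at one-sided 2.5% rejects at 9 or more events, with power 0.86. That is higher than the paired 0.58.

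**Where the paired table gains.** Now suppose no product effect, but a sicker population with 6% on each side, again 6% + 6% = 12%. The literature test sees the same 12% against 4% and signals an excess with the same probability, 0.86. The paired test has m = a = 0.06 × 0.94 = 0.0564 and rejects in either direction with probability 0.024. The literature comparison cannot tell the two situations apart. The within-patient comparison can.

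**The case against.** Several points against this stand.

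- A reader might infer that the side of events is never collected and the comparison is lost. The documents do not support that. The visit lists are headings, and sections 8.2.2 and 11.1 refer to separate event forms whose fields are not given. Since graft side is recorded, an event with a documented location could be paired later.
- A reader might infer that the paired test is more powerful than the literature comparison. Pitting one-sided events in the paired test against all events in the literature test would suggest so: 20% against 28% has power 0.45, and 30% against 38% has 0.38. But section 9.2 compares the nature of events as well as their frequency, and for the same class of event the order reverses.
- Some side information already exists. The panel reads each level unilaterally, and its fusion grade requires absence of screw or rod fracture or loosening. Pain drawings show where pain lies. These are efficacy and pain readings, not adverse events, and no left-right safety analysis is attached to them.
- Relation to the product is not simply left to surgeons' suspicion. Section 7.9 has events reported to the principal investigator and evaluated, with suspected relations discussed with the ethics committee. It does not say who judges relatedness.
- Many events will not have a side. Appendix B uses one midline incision, and section 7.8 says effects of the two sides cannot be separated after revision surgery. Systemic events have no side at all.

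None of these supplies the missing analysis. The analyses in section 9.3 that may touch complications (comparison with the AxA trial, risk-factor regression) do not compare the two graft sides for events.

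**Conclusion.** The point holds as a gap in the planned analysis. The relation of events with MagnetOs is part of a primary outcome, yet section 9.2 offers only tables and an external comparison, and no listed event or X-ray item asks for side. The gain from closing the gap is a concurrent randomised control that removes case-mix bias for local events. It is not extra power: about 0.10 for 5% against 2% and 0.58 for 10% against 2%, assuming independent sides, 100 patients and event rates that are illustrative. The comparison would therefore detect only large imbalances and is mainly descriptive. It could not by itself establish non-inferiority for safety, and it says nothing about events that cannot be assigned to a side. The change is worth making because it is cheap and completes a stated primary outcome.

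**What to change.** 1. Check the adverse event and SAE forms for a location field. If there is none, add one: left, right, midline or both, not assignable. Enter it as a factual location, not as a judgement of relatedness. Add the same field to the X-ray failure item.
2. Record CT heterotopic ossification by side, preferably by the blinded panel, so that at least one local safety sign is read without knowledge of the allocation.
3. In section 9.2 add a supportive table: patients with a local event on the MagnetOs side only, on the autograft side only, on both sides, and with events that cannot be assigned. Give an exact McNemar test and an exact 95% interval for the share of one-side-only patients whose event lay on the MagnetOs side.
4. Leave out donor-site events at the harvested crest. Harvest normally follows the autograft side, so counting them would build in a difference that is not about the material in the fusion bed. Define the exclusion in advance, because harvest preferably uses the same incision and some collections or pain will need a rule.
5. Keep the literature comparison as description.

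Cost: one form field, one CT item and one table, with no change to treatment, visits or sample size. Limits to state with the table: few events, an unassignable remainder (midline wound events, revisions), and side entered largely by surgeons who know the allocation.
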